2. If patients meet criteria for treatment failure status, their dose of inhaled corticosteroids will be increased to the dose they were receiving at visit 4 (800 $\mu\text{g}/\text{day}$) delivered by an open-label inhaler. Study inhalers of corticosteroids (or its placebo) will be returned to the clinical center. If they meet the criteria detailed in Section VI, they will be treated with appropriate rescue algorithms for an asthma exacerbation. Study inhalers of salmeterol (or placebo) will be continued unless the physician can document that treatment failure status was causally related to taking this medication. They will continue to participate in the study until its termination (intent-to-treat analysis), but no further reductions in inhaled corticosteroid dose will be attempted during this time period. For safety reasons, all subjects will be seen within one week ($\pm 3\text{d}$) from the day they were categorized as achieving treatment failure status. Following this "safety" visit, subsequent protocol visits will continue in accordance with the visit schedule established at Visit 1 (see SOCS/SLIC MOP for details concerning possible replacement of scheduled protocol visits with treatment failure related visits).

IV. OUTCOME VARIABLES

The primary outcome variable will be the time to treatment failure. It will be evaluated using a Kaplan-Meier survival analysis. Secondary outcome indicators will include comparisons of FEV₁, mean peak flow variability (PM-AM peak flow difference normalized by the average of the AM and PM peak flow), methacholine airway responsiveness following premedication with salmeterol (evaluation of bronchoprotective effect), asthma symptom scores, quality of life, and rescue medication use at visits 5-11 to those obtained at visit 4.

Daily data obtained from post-randomization diary cards will be summarized and analyzed as averages. Because subjects are instructed to withhold their study salmeterol (or placebo) for 12 hours prior to a visit, the affected peak flow values will be excluded.

V. PROTOCOL

A. Subjects

1. **Sample size.** This trial has a target sample size of 150 randomized patients, with 20 in Group A, 65 in Group B, and 65 in Group C. See section X.F for the derivation of this sample size.

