The strata of a particular patient are noted and the marginal frequencies of these strata are summed for each treatment arm. Then the patient is assigned to that treatment arm which has the smallest sum of marginal frequencies^[16].

E. Statistical Analysis

The primary response variables in this study are time and occurrence of treatment failure after visit 5, where treatment failure is defined in Section III. Kaplan-Meier survival curves will be constructed for the three treatment arms. Statistical tests, such as the logrank test and the generalized Wilcoxon test, will be applied to compare the survival curves of the groups.

In addition, a proportional hazards regression analysis will be applied, which allows for comparing the survival curves of the groups in the presence of other covariates. In this type of analysis the hazard function at time t is modelled as

$$h(t; \mathbf{x}) = h_0(t)\exp(\mathbf{x}^T\xi)$$

where

$h_0(t)$ is the unspecified baseline hazard,

$\mathbf{x} = [x_1 \dots x_k]^T$ is a vector of explanatory variables, and

$\xi = [\xi_1 \dots \xi_k]^T$ is a vector of unknown parameters.

The vector \mathbf{x} will include indicator variables for treatment assignment, Clinical Center, and treatment \times center interactions. The assumption of proportional hazards is important for the logrank test and the proportional hazards regression. This will be assessed via graphical procedures (comparing log survival plots) and statistical tests (including time-dependent covariates in the proportional hazards regression and testing for significance).

Safety of methacholine challenge will be examined by analyzing the frequency of adverse events following clinic visits at which methacholine challenge is performed, compared with the frequency following visits at which it is not. McNemar's test will be applied for this purpose because of the correlated responses within each subject. The efficacy of methacholine challenge will be analyzed by correlating PC_{20} with other measures of asthma outcome, such as AM and PM PEF, FEV_1 , symptom scores, rescue beta-agonist use, and quality of life scores. Correlation coefficient estimates and confidence intervals, specifically designed for longitudinal data, will be calculated for this purpose. Daily data obtained from post-randomization diary cards will be summarized and analyzed as

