Chervinsky, et al^[19] reported a 60% failure rate for a similar group of patients receiving placebo, so we assume that $\theta_A = 0.60$. Greening, et al^[8] reported a 5% failure rate for a similar group of patients receiving salmeterol and ICS, so we assume that $\theta_B = 0.05$. Although it is anticipated that $\theta_A > \theta_C > \theta_B$, there is no report in the literature as to an anticipated failure rate for Group C. As such, a rate which would be considered clinically significant was discussed at length by the ACRN Steering Committee. The committee agreed that a reduction in the treatment failure rate of Group A by more than 50% would be clearly clinically relevant in this patient population. Therefore, failure rates less than 30% were assumed for Group C in order to calculate the sample size. The Steering Committee also recognized that the eventual choice of a precise failure rate for Group C needed to reflect the relative numbers of asthmatic patients with moderate asthma within the entire asthmatic population in the United States (approximately 25% of the total) in order to set realistic recruitment goals for this disease severity category. After numerous discussions with input from various individuals, the Steering Committee agreed that a 20% treatment failure rate for Group C would be the best choice to address both the clinical

relevance of any observed differences and the patient population disease severity restraints.

It is not of interest to detect failure rates in the other direction, i.e., $\theta_B > \theta_C > \theta_A$, so one-sided tests are used. One interim analysis is planned for this trial when approximately one-half of the randomized patients have completed the trial. Therefore, a significance level of $\alpha = 0.029$ (see Pocock^[18]) will be invoked at each analysis. Using $\beta = 0.20$ (80% statistical power) and allowing for a 10% withdrawal rate, a total of 130 randomized patients are needed in Groups B and C. In order to perform the secondary comparison of Group B versus Group A, the target sample size for Group A will be 20 randomized patients. This comparison of Group C versus Group A will have 80% statistical power based on the assumed failure rates of 20% and 60%, respectively. Thus, the required sample size for this trial is 150 randomized patients.

XI. REFERENCES CITED

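### With 20 against 65 patients, the large-sample log-rank and Wilcoxon tests in X.E run at about 0.038 one-sided for the secondary comparison with Group A, not at the 0.029 set in X.F

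*Protocol*

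**What the plan says.** Protocol V.A sets the arms at 150 patients, "with 20 in Group A, 65 in Group B, and 65 in Group C". X.F makes B versus C the primary comparison and rules out interest in the opposite direction, "so one-sided tests are used". It plans two looks: "One interim analysis is planned for this trial when approximately one-half of the randomized patients have completed the trial". A level of 0.029 "will be invoked at each analysis".

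For the secondary comparison, X.F says that "the target sample size for Group A will be 20 randomized patients". That sentence gives the purpose as comparing B with A. The next one reads "This comparison of Group C versus Group A will have 80% statistical power", "based on the assumed failure rates of 20% and 60%, respectively". The two sentences name different pairs. Either pair is 65 against 20, so the point below applies to both.

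On method, X.E says: "Statistical tests, such as the logrank test and the generalized Wilcoxon test, will be applied to compare the survival curves of the groups". It adds a proportional hazards regression without saying which test statistic will be read from it. Nothing in X.E or X.F treats the small, unequal arm differently from the balanced primary comparison.

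**The concern.** The log-rank statistic is referred to a normal distribution. Under the null, each failure falls in Group A with a probability equal to that group's share of patients still at risk, at first 20/85 = 0.235. A sum of such terms is skewed to the right when the share is well below one half, so large excesses of failures in A occur more often than the normal curve allows. The one-sided test looks in exactly that direction, because more failures in A is what favours salmeterol.

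Protocol V.G explains why Group A exists. If B and C came out alike, it separates a salmeterol effect from patients who needed less inhaled steroid than had been estimated. An inflated error rate here leans towards the steroid-sparing conclusion.

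**Working it through.** **Inputs.** From X.F: one-sided 0.029 (critical value z = 1.896), failure rates of 20% (C) and 60% (A), 10% withdrawal. From V.A: 65 and 20 patients. From X.E: time to failure after visit 5. Assumed, because the protocol does not give it: the common failure rate when the arms do not differ. The range 5% to 60% spans the protocol's own 5%, 20% and 60%.

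**1. The plan's own figure.** The factor 4 printed in X.F equals 1/(p1·p2) for equal arms. For 65:20, p1·p2 = (65/85)(20/85) = 0.180.
- Hazard ratio = log(0.8)/log(0.4) = 0.2435, with natural log −1.4125.
- Expected failures after 10% withdrawal = 58.5 × 0.2 + 18 × 0.6 = 22.5.
- Power = Φ(√(22.5 × 0.180) × 1.4125 − 1.896) = Φ(0.946) = 82.8%. Without withdrawal there are 25 failures and power is 86.4%.
- For 80% power, Group A needs 19 patients (17 without withdrawal).

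So the 20 patients and the 80% power reproduce.

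**2. Size by hand.** The skewness of one term at p = 0.235 is (1 − 2p)/√(p(1 − p)) = 0.529/0.424 = 1.248. At a common failure rate of 20% there are 0.2 × 85 = 17 failures, so the sum has skewness 1.248/√17 = 0.303. The first-order correction to the upper tail is (0.303/6)(1.896² − 1)φ(1.896) = 0.0505 × 2.595 × 0.0661 = 0.0087. This gives 0.029 + 0.0087 ≈ 0.038. It is a rough check only, because it holds the risk share fixed and treats the variance as known.

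**3. Size by simulation.** Exponential failure times, administrative censoring at the end of follow-up, 400,000 null trials per row, rejecting when Z > 1.896 towards more failures in A:

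| Common failure rate | 20 v 65 | 20 v 65, 10% withdrawal | 20 v 65, opposite tail | 65 v 65 |
|---|---|---|---|---|
| 5% | 0.0390 | 0.0401 | 0.0001 | 0.0315 |
| 10% | 0.0413 | 0.0415 | 0.0071 | 0.0294 |
| 20% | 0.0385 | 0.0389 | 0.0182 | 0.0285 |
| 30% | 0.0377 | 0.0381 | 0.0205 | 0.0288 |
| 40% | 0.0374 | 0.0373 | 0.0214 | 0.0291 |
| 50% | 0.0370 | 0.0370 | 0.0225 | 0.0288 |
| 60% | 0.0376 | 0.0376 | 0.0228 | 0.0289 |

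The typical excess is 0.038 − 0.029 = 0.009, and 0.038/0.029 = 1.31.

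**4. Cause and alternatives.**
- The same 85 patients split 42/43 give 0.029 to 0.030 at rates of 20% to 60%, so the imbalance is the cause.
- The Gehan form of the generalized Wilcoxon test gives about 0.038. The log-rank with ties by day gives 0.038 to 0.0395.
- A permutation log-rank gives 0.0295 (4,000 trials, rate 30%).
- From an unadjusted proportional hazards model, the signed likelihood-ratio test gives 0.025 to 0.031 and the Wald test 0.030 to 0.036.

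**5. Power at 20% against 60%.** The large-sample log-rank has simulated power of 94.5% (93.5% with withdrawal). The permutation log-rank has about 91% to 92%. Both exceed the formula's 82.8%, which is an approximation.

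**6. Two looks, if the comparison were also tested at the interim.** At about 10 against 33 the interim size is about 0.042. The chance of rejecting at either look is about 0.065, against 0.048 for two looks that each truly hold 0.029.

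**The case against.** The best defence is that X.F gives 0.029 as a nominal level and promises no finite-sample size, and that the list of tests in X.E is open. A permutation p-value could be adopted later without contradicting the protocol. This stands to the extent that 0.029 is not miscalculated and X.F contains no false figure on this point. It does not remove the concern, because both tests actually named share the skew.

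Second, proportional hazards regression is also planned, and its likelihood-ratio test stays near 0.029. This stands too. A reader might infer that the comparison itself must run above its level, but the excess belongs to particular statistics. The protocol does not say which one decides.

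Third, the comparison is secondary, the excess is about one percentage point, and power is high, so only a result near the boundary would change. This is fair and limits the weight of the point.

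Two further inferences go beyond the text. The two-look figure of 0.065 might be read as the plan's actual error rate, but X.F does not say that the comparison with Group A is tested at the interim. V.G might be read as saying that the trial cannot be interpreted without Group A, but its statement is conditional on B and C having identical outcomes.

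**Conclusion.** The point holds for the large-sample, one-sided log-rank and generalized Wilcoxon tests of the 20-patient Group A against an arm of 65. Size per analysis is about 0.038 (0.037 to 0.042) instead of 0.029, in the direction favouring salmeterol. The result rests on constant hazards, exchangeable patients without centre effects or minimisation, and an assumed common failure rate. The excess appears at every rate from 5% to 60%, so it does not depend on that last choice. The primary B versus C test is essentially sound: 0.0285 to 0.0294 at rates of 10% and above, and 0.0315 at 5%. This is a modest, correctable defect in a secondary comparison, worth settling before unblinding. It does not threaten the trial's main conclusion.

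**What to change.** State in X.E or X.F that comparisons with Group A are tested one-sided at 0.029 by one of two methods, chosen in advance:

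- a permutation log-rank p-value, with labels permuted within strata where numbers allow; or
- the signed likelihood-ratio test from the proportional hazards model.

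Keep the large-sample log-rank for B versus C. Describe the permutation test as approximate, not exact. Under X.C and X.D, Group A is formed at visit 4, while B and C are formed at visit 5 by adaptive balancing within centre and subgroup, and a free shuffle of labels does not reproduce that process.

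In the same edit, reconcile the two sentences of X.F that name different secondary comparisons, and say whether the comparison with Group A is tested at the interim.

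The cost is a few sentences and little computing. The permutation test gives up about 2 points of simulated power (roughly 94% to 92% at 20% against 60%), which still exceeds the stated 80%. Power was not simulated for the likelihood-ratio option. No patient numbers or procedures change.
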